Managing anesthesiologists will be those usually composing the team caring for abdominal surgery patients at the participating sites. Anesthesiologists will be randomized into two groups, caring only for either controls or interventional patients, to minimize contamination, i.e., avoid anesthesiologists being exposed to the bundle and then treating control patients. The site PI or study coordinator will be available in the operating room to monitor and provide support with the interventions. This phase will consist of two components (Fig. 1):

A. PEEP and Lung Recruitment - Mechanical Ventilation with Individualized PEEP:

Perioperative lung expansion will be accomplished by PEEP individualization through maximization of the patient's respiratory system compliance (C_{RS}). This corresponds to the minimization of driving pressures, i.e., the difference between plateau pressure and PEEP during mechanical ventilation. This **maximal compliance strategy** will be started immediately after induction and repeated at least hourly throughout the surgery (see Appendix III for additional details).

PEEP individualization will be determined by a recruitment maneuver followed by a decremental PEEP titration (Fig. 3). The stepwise **recruitment maneuver** will consist of the increase of PEEP from 5 to 20 cmH₂O in 5 cmH₂O steps of 30-sec each, as long as the patient's plateau pressure (P_{plat}) =30-32 cmH₂O (PEEP can be increased by 2-3 cmH₂O instead of by 5 cmH₂O to achieve P_{plat} =30-32 cmH₂O). Starting at this maximally achieved PEEP, PEEP will be decreased in 3 cmH₂O steps of 45-75 sec until a maximum C_{RS} is identified by a reduction in C_{RS} at a lower PEEP following a larger C_{RS} at a higher PEEP (Fig. 3). The minimum PEEP along the decremental steps will be 2 cmH₂O. Once the PEEP for maximal C_{RS} is identified, the largest PEEP level achieved during the recruitment maneuver will be used for 30-sec (in order to reinforce lung recruitment), followed by setting PEEP as the value that maximized C_{RS} . The procedure will be repeated on an hourly basis, and following any significant event producing a $\geq 15\%$ reduction in C_{RS} (e.g., significant change in surgical table position, application of surgical retractors, endotracheal tube disconnection, endotracheal tube suction). Similar adjustments will be performed in

[figure not shown]

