Participants in the control group will also be visited (in-person or videoconference) or called in the preoperative settings, post-anesthesia care unit, and postoperatively at a frequency equivalent to that of the intervention group to reduce the likelihood of bias related to less personal attention. At those points, patients will be greeted, and a generic conversation held.

Study Design Aspects Relevant To All Participants:

With the exception of the specific intervention elements, anesthetic and postoperative management will follow each participating site's routine clinical practice, according to

the choices of the primary clinical team caring for the patients. Fluid therapy and intraoperative fluid balance (crystalloids, colloids, and volume loss) will be recorded for analysis. Participants will receive standard local measures to maintain oxygenation, hemoglobin, core temperature, blood pressure and heart rate. Postoperative analgesia will be typically provided by epidural infusion (bupivacaine \pm opioid) or intravenous patient controlled opioid infusion. Oxygen supplementation postoperatively is recommended to be administered if $\text{SpO}_2 < 94\%$ (measured at rest in room air).

Blood Biomarker Analysis and Biobank:

We will collect blood samples perioperatively at three specific time points (before surgical incision, at extubation $\pm 30\text{min}$ at the end of surgery, and $24 \pm 12\text{h}$ after extubation). Blood collection (10mL at each time point for a total of maximum 30 mL per patient) will be synchronized with routine blood draws whenever possible to prevent extra needle sticks for the patient. All samples will be sent to the University of Colorado for storage as the PRIME-AIR biorepository and they will be analyzed for biomarkers of lung injury under the supervision of the study co-PI, [name]. The 10mL blood samples will be distributed in EDTA tubes (7.5mL) for plasma collection and PAXgene tubes (2.5mL) for RNA collection. The EDTA samples will be centrifuged at 1,000-2,000 rpm for 10 min, plasma volume aliquoted (0.5 mL aliquots), and frozen at 80°C until analysis. Following conclusion of the study and unless patients have opted out, samples of the PRIME-AIR biorepository will be submitted to the NHLBI Biologic Specimen and Data Repository (BioLINCC) for the creation of a biobank for future studies on PPCs.

Study Outcomes

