Clinically important differences for primary and secondary outcomes: Because a large number of patients are affected by PPCs and undergo abdominal surgery, even small percent differences in the outcomes to be studied represent a large absolute number of patients that could be affected by the studied intervention. Accordingly, we will consider clinically significant: (a) a 10% difference in the primary outcome of the study (the row mean score test of a Cochran-Mantel-Haenszel, which incorporates both the frequency and highest grade of severity of PPCs during the first 7 days after surgery; (b) 5% difference in the rate of composite or isolated PPCs; (c) 5% difference in the rate of intraoperative and major extrapulmonary complications; (d) a difference of 12h in the length of postoperative oxygen therapy/other respiratory support; (e) a difference of half-day in the length of hospital stay.

Plasma biomarkers. We hypothesize that the PRIME-AIR bundle will minimize lung mechanical injury and inflammation by reducing overinflation and atelectasis.

Accordingly, it will reduce plasma levels of biomarkers of inflammatory, epithelial and endothelial injury. Plasma will be collected from all patients for analysis of a focused panel of plasma biomarkers of inflammation (cytokines IL-6, IL-8); epithelial injury (the soluble form of the receptor for advanced glycation end-products, RAGE, and club cell protein 16, CC16), and endothelial injury (angiopoietin-2, Ang-2). We will compare biomarker levels in the PRIME-AIR bundle vs. control groups before, at the end of and 24h after surgery. Blood collection in this aim will not only allow for the biomarkers analysis, but also for the creation of a biobank for future studies on PPCs.

Blinding: Because the intraoperative and postoperative interventions cannot be blinded, each site will have at least 2 members of the research team: one to perform the randomization, education, and implementation of the protocol in the operating room and postoperative incentive spirometry/mobilization during hospital visits (in-person or videoconference); and another, blinded to patient allocation, to assess PPCs and all other outcomes -with information obtained from the participant's medical chart and phone calls to the participant (phone script in Attachments/Insight). Investigators performing biomarker assays will also be blinded to study group.

VI. STATISTICAL ANALYSIS

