We will also compare biological measures of lung function and injury between the interventions: (1) lung mechanics and gas exchange; and (2) plasma biomarkers of lung injury at baseline, end of and 24±4h after surgery (see secondary outcomes).

Minimizing bias in outcome assessment: Study of each subject will involve at least 2 investigators per center: one to perform the randomization and implementation of the protocol in the operating room, and another, blinded to patient allocation, to assess for postoperative complications.

Analytic approach - secondary endpoints: The type of variable of the secondary outcome determines the approach used, as listed in Table 6 below:

Table 6. Approach for primary analysis according to the type of variable	
Type of Variable	Approach for Primary Analysis

Binary	For rare events ($\leq 5\%$): Fisher's Exact test For more common events ($>5\%$): Logistic regression (to allow for stratification by site)
Categorical (> 2 categories)	Cochran-Mantel-Haenszel test
Continuous	van Elteren test (an extension of the Wilcoxon Rank Sum test to allow for stratification by site)
Time to death	Cox Proportional Hazards Model
Repeated continuous outcomes (e.g. PROMIS® measures)	Mixed model Analysis of Variance

Additional analyses to fully explore the data will be specified in the SAP.

Interim analyses: We will perform two interim analyses after approximately 1/3 and 2/3 of participants have completed the 7-day follow up. Efficacy will be assessed using a Haybittle-Peto boundary of 0.001 at each analysis. We will be doing a futility analysis at the second interim analyses as well.

VII. RISKS AND DISCOMFORTS

The estimated risks and discomforts involved with participation in this study include:

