- Thromboembolism: A new blood clot or thrombus or embolus reducing blood circulation within the venous or arterial systems with the exception of the pulmonary venous system.
- Pulmonary embolism: A new blood clot or thrombus or embolus reducing blood circulation within the venous pulmonary system.

- Other (describe):
 - Length of stay in the post-anesthesia care unit
 - Length of postoperative oxygen therapy/other respiratory support
 - Unexpected admission to ICU
 - Length of ICU stay
 - Length of hospital stay
 - Hospital readmission(s) after initial discharge
 - Patient-Reported Outcomes Measurements (PROMIS®) short forms (Appendix IV) addressing: Dyspnea Characteristics, Severity and Functional Limitations; and Fatigue, at days 7, 30 and 90 after the day of surgery, compared to before surgery.
 - Plasma concentrations (raw and ratios compared to individual's levels before surgery) of selected biomarkers of inflammatory, epithelial and endothelial injury.

Patient Education for the PRIME-AIR study

Our **goal** with this study is to reduce respiratory complications after abdominal surgery. These complications are one of the main reasons why patients like you have a slower recovery and stay in the hospital longer. We think that keeping your lungs 'open' (well filled with air) may improve the amount of oxygen in your blood, reduce the risk of lung infection and other respiratory complications and lower the need for breathing treatments.

What we will do:

- **Before surgery:** We will teach you breathing exercises (incentive spirometry).
- **During surgery:** We will use the ventilator (the machine that helps you breathe during surgery) to keep your lungs well inflated during your surgery. We will also make sure that your muscles are not weak at the end of surgery. You will be under anesthesia for this part and not aware of it.
- **After surgery:** We will work with you so that you do your breathing exercises well after surgery. We will also check that you are getting out of bed and starting to walk as expected. We will check on you and your medical chart to record your respiratory symptoms, complications and treatments. We will do this several times every day after your surgery until you leave the hospital or up to 7 days after your surgery. We will follow up with you by calling you at home or visiting you at the hospital after 7, 30 and 90 **days** have passed after your surgery.

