6.1.4 General Analysis Approach

For the primary endpoint (the highest value on 5-Point PPC Grade, 0 to 4 through POD7), the Row Mean Score test from a Cochran-Mantel-Haenszel test stratified by site is used. Differences in the Row Mean Score and the associated 95% confidence limit are provided.

A Cochran-Mantel-Haenszel test (with site as a stratification variable) is used for binary variables. The relative risk and the associated 95% confidence limit will be provided.

A standard t-test is used for continuous variables and the difference between the groups and the associated 95% confidence will be provided. This approach provides results that are easier to understand than those using a difference estimate derived from a model adjusting for site, which would not be the same as the difference between the two observed means.

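### For Aim 2 the protocol names only raw biomarker levels and ratios to baseline; a baseline-adjusted log-scale analysis should be specified as principal

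*Protocol*

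**What the plan says.** Specific Aim 2 (Protocol section II) asks whether the bundle lowers plasma markers of lung injury. The Plasma biomarkers paragraph in section V names five (IL-6, IL-8, RAGE, CC16, Ang-2) and states the comparison: "We will compare biomarker levels in the PRIME-AIR bundle vs. control groups before, at the end of and 24h after surgery". It also says "Plasma will be collected from all patients for analysis". Appendix I gives the form in which concentrations are expressed: "raw and ratios compared to individual's levels before surgery". None of these places names a test.

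Protocol section VI mentions the biomarkers again and refers the reader to the secondary outcomes, but the secondary and exploratory lists in section V do not contain them. Table 6 assigns a site-stratified rank test (van Elteren) to continuous outcomes and "Mixed model Analysis of Variance" to repeated continuous outcomes, with PROMIS as the example. It does not say which row covers biomarkers or how the pre-surgery value enters.

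The SAP prevails over the protocol. Its section 4.1 confines it to the PPC analysis and secondary outcomes, and its section 4.5 lists no biomarkers. Its general rule in 6.1.4 is "A standard t-test is used for continuous variables", without adjustment.

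On timing, Protocol section V (Blood Biomarker Analysis and Biobank) places the samples "before surgical incision, at extubation" and about a day later. The intraoperative PEEP strategy "will be started immediately after induction and repeated at least hourly throughout the surgery". The window for the last sample is 24±12 h after extubation in section V but 24±4 h after surgery in section VI.

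**The concern.** The two named measures sit at opposite ends of a scale. Analysing the post-surgery concentration alone ignores the pre-surgery value, so stable differences between patients stay in the error term. Dividing by the pre-surgery value fixes the log-scale slope on baseline at exactly 1, which adds baseline noise whenever the true slope is lower. If the markers are right-skewed, a t-test on either measure without logs loses further power. A model of log concentration with log baseline as a covariate estimates the slope instead of fixing it at 0 or 1.

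At stake is precision for one of the trial's two specific aims, from samples already planned for everyone. With two scales named and neither called principal, the reader also cannot tell in advance which result will count.

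**Working it through.** **Plan's own figure.** There is none for this aim. The only power statement in either document (93%) concerns the primary PPC outcome, which this point does not touch.

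**Inputs from the documents.** Plasma from all patients; 375 per group, 750 in total, allocated 1:1; one sample before incision and two afterwards. **Inputs assumed.** Correlation ρ between log baseline and log follow-up, and the SD of logs; the documents give neither. SDs are taken as equal at baseline and follow-up.

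**Formulas.** Variance of the between-arm difference on the log scale, relative to follow-up alone:

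- follow-up alone: 1
- log ratio to baseline: 2(1−ρ)
- adjusted for log baseline (ANCOVA): 1−ρ²

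So ANCOVA over log ratio is (1−ρ²)/[2(1−ρ)] = (1+ρ)/2, and ANCOVA over follow-up alone is 1−ρ². Both are below 1 for 0 < ρ < 1.

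| ρ (assumed) | Follow-up alone | Log ratio | ANCOVA | Saving vs better scale | Saving vs worse scale |
|---|---|---|---|---|---|
| 0.3 | 1 | 1.40 | 0.91 | 1 − 0.91/1 = 9% | 1 − 0.91/1.40 = 35% |
| 0.5 | 1 | 1.00 | 0.75 | 25% | 25% |
| 0.7 | 1 | 0.60 | 0.51 | 1 − 0.51/0.60 = 15% | 1 − 0.51/1 = 49% |
| 0.9 | 1 | 0.20 | 0.19 | 1 − 0.19/0.20 = 5% | 1 − 0.19/1 = 81% |

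Against the better scale the saving peaks at ρ = 0.5. There, 750 patients analysed on either named scale carry the information of 750 × 0.75, or about 562, analysed with baseline adjustment.

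With unequal SDs the percentages change but the direction does not. Follow-up alone fixes the slope at 0, the log ratio fixes it at 1 and ANCOVA estimates it, so in large samples ANCOVA is no less precise than either.

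**Simulation on unlogged data.** 375 per arm, log-normal values, one follow-up time, no site effect, true effect 0.2 SD on the log scale, 2000 runs per setting. The rank test is an unstratified Wilcoxon, standing in for van Elteren. Power:

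| SD of logs, ρ | t-test raw | t-test ratio | Rank raw | Rank ratio | ANCOVA on logs |
|---|---|---|---|---|---|
| 1.0, 0.3 | 56% | 37% | 75% | 61% | 81% |
| 1.0, 0.5 | 56% | 56% | 74% | 76% | 87% |
| 1.0, 0.7 | 58% | 85% | 76% | 93% | 97% |
| 0.5, 0.5 | 74% | 74% | 77% | 77% | 89% |

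Taking logs matters for a t-test or mixed model. A rank test gives the same result on a measure and its log, so under van Elteren the cost comes from the missing baseline adjustment.

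**Baseline timing.** A sample can be drawn before incision yet after induction, and the PEEP strategy begins at that point. Some baselines may therefore follow the first recruitment maneuver. If the bundle has already shifted the marker, both the ratio and the adjusted analysis would remove part of its effect; an unadjusted comparison would not.

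**The case against.** The strongest reply is that Appendix I defines how outcomes are expressed and does not choose a method. A reader might infer that the protocol picked raw values and ratios in preference to baseline adjustment. The documents do not support that, because no test is named. Biomarkers measured at three times fit the repeated-outcomes row of Table 6 well, so a mixed model may already be intended. This stands, but it does not close the gap: a mixed model recovers the gain only if baseline is a covariate or the baseline means are constrained equal, and neither is stated.

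A separate Aim 2 plan may exist, since the SAP limits itself to the PPC analysis and heads section 5 as additional measurements for the primary paper. None was among the documents reviewed; if there is one, the specification belongs there.

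Three further readings go too far:

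- **Savings of 35%, 49% or 81%.** These are measured against whichever named scale is worse at that ρ. The ratio already uses baseline and loses only about 5% at ρ = 0.9.
- **Twice as many tests.** Five markers, two post-surgery times and two scales would give 20 comparisons instead of 10, but nothing says both scales will be formally tested. SAP 6.6 already leaves secondary and exploratory P-values unadjusted, and denies them significance if the primary endpoint fails.
- **An invalid comparison.** Given a sound baseline sample, both named scales allow a valid randomised comparison. The issue is efficiency.

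**Conclusion.** The point holds as a minor one about efficiency and specification. Neither document specifies a baseline-adjusted log-scale analysis for the Aim 2 biomarkers, and the only measures named are raw concentrations and ratios to the pre-surgery level. Against the better of these, adjustment would cut variance by about 9%, 25%, 15% or 5% at ρ = 0.3, 0.5, 0.7 or 0.9, and by more against the other. These figures rest on equal SDs on the log scale and on assumed correlations, so the actual loss cannot be fixed from the documents. No stated power figure is wrong, and the primary outcome and its analysis are unaffected.

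**What to change.** - **Principal analysis.** For each biomarker, fit a mixed model of log concentration at end of surgery and 24 h with arm, time, arm-by-time, log pre-surgery level and site. Report the arm effect at each time as a geometric mean ratio with its confidence interval. Keep raw concentrations and ratios to baseline as descriptive summaries.
- **Baseline timing.** Record, where available, when the baseline sample was drawn relative to the first recruitment maneuver. Keep all patients in the main analysis and add a sensitivity analysis without baseline adjustment, or one limited to samples drawn before the maneuver. The unadjusted version is simpler, because usual care has no scheduled maneuver against which to time a sample. Excluding patients from the main analysis could give back the precision gained, and SAP 4.1 reports 751 participants as already studied, so sampling cannot be changed.
- **Sampling window.** Reconcile the 24±12 h and 24±4 h statements in Protocol sections V and VI, including whether time runs from extubation or from surgery.

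The cost is a short paragraph in the biomarker analysis plan and slight extra analysis work. No new samples are needed.

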Appendix III - Maximal compliance strategy for PEEP titration

Ventilatory Settings	
 • Volume-controlled ventilation, square flow-waveform • $V_T=7$ mL/kgPBW, adjustment to 6-8 ml/kg PBW if required • RR=12 bpm titrated to $P_{etCO_2}=35-45$ mmHg • $F_iO_2 \geq 0.4$ to $SpO_2 \geq 96\%$ • I:E ratio started at 1:2 and adjusted if necessary to the patient's physiology • Inspiratory pause 20% • Maximum acceptable plateau pressure 30 cmH₂O, V_T will be reduced if needed to achieve that value
When	
 • Immediately following intubation; • After any intervention potentially associated with lung collapse such as application of surgical retractors, pneumoperitoneum insufflation/deflation, disconnection of the endotracheal tube, tracheal suctioning, Trendelenburg position, or if the static respiratory system compliance is reduced by $\geq 15\%$; • Otherwise, hourly trials will be done counted from the last trial.
Recruitment maneuver	
 • Assure adequate muscle paralysis, volemia and hemodynamics • Recruitment maneuver: This will consist of a stepwise incremental PEEP maneuver: In volume-controlled ventilation, starting from a PEEP=0 cmH₂O, increase PEEP in steps of 5 cmH₂O until $P_{pl}=30-32$ cmH₂O (i.e., PEEP= 5, 10, 15 and 20 cmH₂O). Remain for at least 30 s at each step. If there is any concern for cardiopulmonary instability at the last step, this can be reduced to 2-3 cmH₂O aiming for the targeted P_{pl} range. Address hemodynamic issues if they occur before advancing to a higher PEEP step, and reduce PEEP if needed to prioritize hemodynamic management before proceeding. Recruitment maneuvers will be performed before the spontaneous breathing trial preceding extubation. The maneuver will be interrupted if the patient becomes bradycardic or tachycardic (< 60 or > 140 beats per minute), develops a new arrhythmia, becomes hypotensive (systolic blood pressure < 80 mmHg) or hypoxemic ($SpO_2 < 85\%$). Incidence of out-of-protocol change of ventilatory settings to assure $SpO_2 > 90\%$, $P_{pl} \leq 30$ cmH₂O, or at the discretion of the patient's anesthesia providers will be recorded.
Decremental PEEP Titration	Performed in steps of 45-75 s each until a drop in the static C_{rs} is observed. At this point the PEEP is set at the value which reached the recruitment range of $P_{plateau} = 30-32$ cmH ₂ O for 30 sec after which the chosen PEEP is set to continue ventilation. If a value lower than 20 cmH ₂ O was used as the maximal level of recruitment, that will be the starting PEEP for the decremental titration.

Appendix IV – PROMIS Forms

Short Form Fatigue:

PROMIS Short Form v1.0 - Fatigue - 13a - 20Feb2017

http://www.healthmeasures.net/index.php?option=com_instruments&view=measure&id=822&Itemid=992

PROMIS® Item Bank v1.0 – Fatigue – Short Form 13a (FACIT-Fatigue)

Fatigue – Short Form 13a (FACIT-Fatigue)

Please respond to each question or statement by marking one box per row.

During the past 7 days...		Not at all	A little bit	Somewhat	Quite a bit	Very much
		1	2	3	4	5
H17	I feel fatigued					
H12	I feel weak all over					
AN1	I feel listless ("washed out").....					
AN2	I feel tired					
AN3	I have trouble starting things because I am tired.....					
AN4	I have trouble finishing things because I am tired.....					
AN5	I have energy					
AN7	I am able to do my usual activities.....					
AN8	I need to sleep during the day.....					
AN12	I am too tired to eat					
AN14	I need help doing my usual activities					
AN15	I am frustrated by being too tired to do the things I want to do.....					
AN16	I have to limit my social activity because I am tired.....					

Short Form Dyspnea Functional Limitations:

PROMIS Short Form v1.0 - Dyspnea Functional Limitations - 10a 02Sept2016

http://www.healthmeasures.net/index.php?option=com_instruments&view=measure&id=774&Itemid=992

PROMIS Item Bank v1.0 – Dyspnea Functional Limitations – Short Form 10a

Dyspnea Functional Limitations - Short Form 10a

Please respond to each question or statement by marking one box per row.

Considering your shortness of breath over the past 7 days, rate the amount of difficulty you had when doing the following activities...		No difficulty	A little difficulty	Some difficulty	Much difficulty	I did not do this in the past 7 days
DYSFL001	Dressing yourself without help	 0	 1	 2	 3	 X
DYSFL002	Walking 50 steps/paces on flat ground at a normal speed without stopping	 0	 1	 2	 3	 X
DYSFL003	Walking up 20 stairs (2 flights) without stopping	 0	 1	 2	 3	 X
DYSFL004	Preparing meals	 0	 1	 2	 3	 X
DYSFL005	Washing dishes.....	 0	 1	 2	 3	 X
DYSFL006	Sweeping or mopping.....	 0	 1	 2	 3	 X
DYSFL007	Making a bed.....	 0	 1	 2	 3	 X
DYSFL008	Lifting something weighing 10-20 lbs (about 4.5-9kg, like a large bag of groceries).....	 0	 1	 2	 3	 X
DYSFL009	Carrying something weighing 10-20 lbs (about 4.5-9kg, like a large bag of groceries) from one room to another.....	 0	 1	 2	 3	 X
DYSFL010	Walking (faster than your usual speed) for $\frac{1}{2}$ mile (almost 1 km) without stopping	 0	 1	 2	 3	 X
